Using an ANOVA framework for estimating sample size for a 1x3 factorial design (Specific Aim A: complete responder, partial responder, and non-responder), we calculate the sample required to detect within-subject changes in upper airway function (e.g., the severity of upper airway obstruction during DISE as reflected by measurements of pharyngeal collapsibility, P_{CRIT}), based on published data demonstrating decreases in pharyngeal collapsibility (P_{CRIT}) of $\sim 3.5 \pm 2.0$ cmH₂O during stimulation ³⁴. This response accounts for $\sim 24\%$ of the total variance (η^2), which yields an effect size (f) of ~ 0.40 . Our data also demonstrate within-subject correlations of at least 0.5 for repeated P_{CRIT} measurements ^{69,70}. Using these parameters, we calculated that 15 subjects would be required to detect significant differences in each of 3 responder categories with an alpha of 0.05 and a power of 90%. To account for measurements in both sexes, subject attrition, and incomplete measurements, we propose an 'n' of 45 subjects to complete the protocol. We also plan to examine the effects of sex and BMI on this outcome, which will require an additional 30-60 subjects (total n = 100) for the entire protocol. This sample size will allow us sufficient power to detect substantial effects of stimulation on tongue morphology (Specific Aim B) and effects of craniofacial structures on tidal airflow and markers of airway collapsibility (Specific Aim C).

d. Early stopping rules.

- This is a low-risk study designed to examine underlying mechanisms of action of lingual and hypoglossal nerve stimulation treatment in patients with obstructive sleep apnea. Since the protocol will involve temporarily stopping HGNS treatment for 5 days, one risk includes excessive daytime sleepiness. We have attempted to minimize subject risk with the strict exclusion criterion, "Patients who have fallen asleep while during resulting in an accident or 'near miss' accident within 1 year prior to device implantation." In addition, we will advise patients against driving and operating heavy machinery during this 5-7 night washout period and we will perform a check-in call after the first 2 nights without therapy. We will specifically ask patients if they have fallen asleep while driving, and will withdraw any patients answering yes. We also recognize and inform each subject of his/her right to withdraw from the clinical study at any time.

8. Risks

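### A 24% share of total variance does not convert to f of about 0.40; the 24% is probably a mislabelled partial eta-squared, and the 15 subjects fit a design the plan does not describe

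*SAP*

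**What the plan says.** SAP section 7c sets up the sample size as a "1x3 factorial design (Specific Aim A: complete responder, partial responder, and non-responder"), and says of its purpose that "we calculate the sample required to detect within-subject changes in upper airway function", with P_CRIT as the example. It starts from a published fall in P_CRIT during stimulation, attributes to it about 24% "of the total variance" (eta-squared), and continues "which yields an effect size (f) of ~ 0.40". The next sentence adds a further input: "Our data also demonstrate within-subject correlations of at least 0.5". From these, at alpha 0.05 and 90% power, "we calculated that 15 subjects would be required to detect significant differences in each of 3 responder categories".

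The section then proposes 45 subjects, to cover both sexes, attrition and incomplete measurements, and 100 in all so that sex and BMI can be examined. The opening of section 7 names stimulation status, on versus off, as the primary independent variable. No conversion formula is given, and nothing says that the eta-squared is partial or adjusted for the correlation.

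**The concern.** The variance share and f are the only printed effect-size basis for the 15 subjects and the 90% power. Under the usual definition of eta-squared as a share of total variance, one does not give the other, so the sentence cannot be right as it stands.

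The second difficulty is the design. The one calculation that ties the printed figures together treats the three levels as repeated measurements in the same subjects. A patient is a complete, partial or non-responder, and is not measured once under each category. The repeated factor that the SAP names has two levels. A reader therefore cannot tell which test the 90% belongs to, or whether 15 is a total or a number per category. For some of the candidate tests the power is well below 90%.

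**Working it through.** **Inputs, all from SAP section 7 and 7c:** eta-squared about 0.24; f about 0.40; within-subject correlation ρ = 0.5 (stated as a minimum); alpha 0.05; power 90%; three responder categories; stimulation on versus off; n = 15, then 45, then 100. Power is from the noncentral F distribution, with equal groups where there are groups.

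**Step 1: reproduce the printed 15.** For m repeated levels in one group, λ = f²·n·m/(1 − ρ), with m − 1 and (n − 1)(m − 1) degrees of freedom. With f = 0.40, m = 3 and n = 15, λ = 0.16 × 15 × 3/0.5 = 14.4 and power is 90.6%. At n = 14 it is 88.2%. So 15 reproduces, as a total for three repeated levels.

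**Step 2: convert as worded.**
- f = √(η²/(1 − η²)) = √(0.24/0.76) = 0.562, against the printed 0.40.
- In reverse, η² = f²/(1 + f²) = 0.16/1.16 = 0.138, against the printed 0.24.
- Rounding does not close the gap: 23.5% to 24.5% gives f of 0.554 to 0.570.

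**Step 3: convert as a partial, within-subject share.** Here the error variance is the within-subject part, 1 − ρ.
- Partial η² = f²/(f² + 1 − ρ) = 0.16/(0.16 + 0.5) = 0.242, the printed 24%.
- In reverse, f = √(0.24/0.76 × 0.5) = 0.397, the printed 0.40.

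So 24%, 0.40, 0.5, 90% and 15 all belong to one calculation, provided that the 24% is partial and the three levels are repeated.

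**Step 4: put f = 0.40 and ρ = 0.5 into tests that fit the SAP's own design.**

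| Test | λ | Power at the stated number | Total needed for 90% |
|---|---|---|---|
| On versus off, one group | f²·n·2/(1 − ρ) | 82% at 15 | 19 |
| Category by stimulation, three groups | f²·N·2/(1 − ρ) | 68% at 15 in total | 24 |
| One-way on three categories (ρ not used) | f²·N | 64% at 3 × 15 = 45 | 84 |

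The first row also applies if on versus off is tested separately inside a category of 15. If 15 is per category and all 45 are used together, on versus off and category by stimulation both exceed 99%; only the one-way comparison falls short.

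**Step 5: the same tests if 24% really is a share of total variance (f = 0.562).** Three repeated levels would need 9 (92.8%; 88.6% at 8). A one-way comparison at 45 has 91% power. Category by stimulation at 15 in total has 94%.

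**Step 6: the planned total.** The one-way comparison at f = 0.40 is the least favourable of the tests in Step 4. It has 95% power at 100, and 89% at 80, which is 100 less the roughly 20% that section 4b expects not to complete all visits.

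**The case against.** The strongest reply is that there is no numerical error. The section speaks of within-subject change, supplies a correlation, and bases the 15 on the parameters it has listed. Step 3 shows that these parameters agree with one another once the 24% is read as partial. This largely stands, and it is why the label is the likelier error. It remains an inference: the text says total variance, shows no formula, and brings in the correlation only after f has been derived.

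A reader might infer instead that f is wrong and should be 0.56, or that the printed 15 is no guide because f = 0.56 also leads to 15 in other designs. The SAP does not support either. The one-way route to 15 per category makes no use of the correlation that the SAP lists as an input and is not a within-subject test. The interaction route reaches 15 only because groups are held equal; 14 already gives 91%. Neither explains a printed f of 0.40. The match 3 × 15 = 45 is weak evidence too, since 45 is presented as including an allowance for both sexes, attrition and incomplete data.

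It can also be said that the design question is separate from the conversion. That is fair: the low power figures in Step 4 come from the design, not from the variance label. Both concern the same short calculation, however, and one rewrite settles both.

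**Conclusion.** As printed, the variance share and f are inconsistent: 0.56 against 0.40, or 14% against 24%. This is certain for the wording. That the label is at fault, rather than f, is the more probable explanation and rests on the agreement found in Step 3.

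The stated 15 delivers 90% for three repeated levels in the same subjects. That is not the SAP's design. At f = 0.40 and ρ = 0.5, 15 in total gives 82% for on versus off and 68% for category by stimulation, and 45 gives 64% for a one-way comparison of categories. These figures assume equal groups where there are groups, and a correlation of exactly 0.5; a higher correlation would raise the two within-subject figures.

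A reader might go on to infer that the study is too small. The SAP does not support that: at 100 subjects even the one-way comparison has 95% power, and at 80 it has 89%. If the 24% were truly a share of total variance, f = 0.40 would be a conservative entry for the three-repeated-level calculation (15 against 9). No enrolment number has to change on this account, and the severity is minor.

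**What to change.** In section 7c, relabel the 24% as partial (within-subject) eta-squared and show the step: f = √(0.24/0.76 × (1 − 0.5)) = 0.397, about 0.40. Only if the source calculation shows that the 24% is truly a share of total variance, keep that label and print f = 0.56 instead.

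Then name the test that is powered (on versus off, category by stimulation, or a comparison between categories), say whether 15 is per category or in total, and restate n and power for that test. At f = 0.40, ρ = 0.5 and 90% power, the totals are 19, 24 and 84 respectively.

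The cost is two or three rewritten sentences and one rerun of the calculation. The planned total of 100 can stay.

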Characterizing Mechanisms of Upper Airway Obstruction During Drug-Induced Sleep Endoscopy (DISE)

Principal Investigator	[name], MSCR Dept. of Otorhinolaryngology – Head and Neck Surgery [name] [contact] [contact]
Co-Investigators	[name] Dept. of Otorhinolaryngology – Head and Neck Surgery [name] [contact] [contact]
	[name] Dept. of Anesthesiology [name] [contact] [contact]
	[name] Dept. of Otorhinolaryngology – Head and Neck Surgery [name] [contact] [contact]
Regulatory Sponsor	[name] Penn Sleep Center [name] [contact] [contact]
Funding Sponsor	National Institutes of Health (NIH) - National Heart, Lung, & Blood Institute (NHLBI) [name] [contact]
IRB Protocol Number	833511

Initial version 05/30/2019

Amended 06/19/2019

Amended 07/01/2019

Amended 02/11/2020

Amended 03/24/2020

Amended 05/01/2020

Amended 12/15/2021

Amended 07/18/2022

Study Summary

Title	Characterizing Mechanisms of Upper Airway Obstruction During Drug-Induced Sleep Endoscopy (DISE)
Short Title	DISE-CAD
IRB Number	833511
Methodology	Prospective, single cohort
Study Duration	5 years
Number of Subjects	Study A: 100; Study B: 100
Study Center	University of Pennsylvania

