2. **CPAP Level Manipulation:** The nasal pressure will be manipulated to measure pharyngeal cross-sectional area and tidal airflow at various levels of upper airway patency, as previously described⁴⁶⁻⁶⁸. Nasal pressure will be maintained at an elevated holding pressure at which airflow obstruction is abolished, and then dropped step-wise for several breaths to pressures that induce inspiratory flow limitation and complete obstruction.
3. **Pharyngeal Manometry:** In addition to standard sleep monitoring, up to two 7 French Millar catheters (Houston, TX) will be passed perinasally to monitor pharyngeal pressure swings and will be used subsequently as an internal calibration marker for measurements of pharyngeal cross-sectional area on videoendoscopy images during sleep studies^{32,33}. To facilitate this process, we will administer 2% Viscous Lidocaine perinasally before passing the catheter(s).
4. **Ultrasound procedures:** Ultrasound will be performed in each study participant after propofol-induced sleep has been initiated. Measurements during DISE will take about 10 minutes. Images will be acquired with and without stimulation of tongue protrudors.

5. **Lingual Muscle Stimulation (Study B only):**

Patients will have already undergone HGNS implantation and device setting optimization as part of clinical standard-of-care. The Inspire programmer will be used to turn on and off stimulation during DISE and PSG procedures.

b. Study duration and number of study visits required of research participants.

Each participant will be asked to participate for the duration of Visit 1 (1-2 hour clinic visit), Visit 2 (up to one half day for imaging procedures), Visit 3 (baseline overnight sleep study), and Visit 4 (1 half day for DISE procedure). We anticipate that approximately 20% of participants will not be able to complete all of these visits. Participants' participation in these assessments will remain completely voluntary.

We estimate that it will take us about 5 years to collect, process, and fully analyze the ultrasound and DISE study data. Each subject's active participation is anticipated to last for about 1 month.

c. Blinding, including justification for blinding or not blinding the trial, if applicable.

There is no blinding of subjects. Investigators will be blinded before measurement of acquired images to avoid observer confirmation bias.

d. Justification of why participants will not receive routine care or will have current therapy stopped.

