Overnight sleep study will be used to characterize patients' sleep apnea. This test consists of a standardized array of non-invasive sensors applied to the head (EEG), chin and legs (EMGs), upper lip (airflow) the finger (oximetry), and chest/abdomen (respiratory effort, ECG). It records physiologic signals non-invasively that detect apneic episodes and characterize sleep/wake state.

b. Drug and device management

Propofol and equipment for conducting drug-induced sleep endoscopy will be procured and administered by trained endoscopy/operating room staff. The Inspire stimulator will have already been implanted as part of routine clinical care and will be operated by trained staff using the Inspire Programmer.

7. Study Statistics

Our primary independent variable is stimulation status (on versus off). Additional predictors of responses to stimulation will include measurements of tongue and craniofacial morphology.

a. The impact of these independent variables will be examined on the following primary outcome variables:

- Tidal airflow and related flow-surrogates for upper airway collapsibility
- Pharyngeal cross-sectional area in the velo- and oropharynx

b. Secondary outcome variables:

N/A

c. Statistical plan including sample size justification and interim data analysis:

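### Fifteen per responder category is already 45, so 45 cannot also hold the allowances claimed for it, and the effect-size inputs behind 15 conflict with each other

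*SAP*

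**What the plan says.** Section 7c sizes the study with an ANOVA "for a 1x3 factorial design (Specific Aim A: complete responder, partial responder, and non-responder". It says the aim is to detect changes within subjects in upper airway function, such as pharyngeal collapsibility. It gives eta squared of about 24%, an f of about 0.40 said to follow from it, alpha 0.05 and power 90%, and adds: "Our data also demonstrate within-subject correlations of at least 0.5". The result is worded as "15 subjects would be required to detect significant differences in each of 3 responder categories".

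The next sentence reads "To account for measurements in both sexes, subject attrition, and incomplete measurements, we propose an" n "of 45 subjects to complete the protocol". Sex and BMI effects then raise the total to 100. The Study Summary lists "Study A: 100; Study B: 100".

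Two other places bear on this. Section 7 opens: "Our primary independent variable is stimulation status (on versus off"). Section 4b says: "We anticipate that approximately 20% of participants will not be able to complete all of these visits".

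**The concern.** The per-category wording and the allowance sentence cannot both be true. This is the SAP's only quantified power claim, and a reader cannot tell whether the 45 behind it contains a large margin or none.

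The description of the calculation adds to the doubt. A patient belongs to one responder category only, so the three categories are groups of different patients. Yet the aim is a within-subject change and the inputs include a within-subject correlation, which a comparison of separate groups does not use. The within-patient factor that section 7 names has two levels, not three. If the claim cannot be traced to a design, nobody can say later which analysis was powered at 90%.

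**Working it through.** **Inputs.** From section 7c: eta squared 0.24, f 0.40, correlation r of at least 0.5, alpha 0.05, power 0.90, and the figures 15, 45 and 100. From section 7: two stimulation levels. From section 4b: about 20% not completing all visits. Assumptions: categories of equal size; the 20% is applied to the DISE outcome, which is an upper bound because it counts any missed visit.

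**Method.** Power is the probability that a noncentral F variable exceeds the 95th percentile of the central F, with noncentrality λ.

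**1. The allowance inside 45.**
- 15 per category: 15 × 3 = 45, so the allowance is 45 − 45 = 0. If 45 were enrolled, 45 × 0.8 = 36 would complete.
- 15 in total: the allowance is 45 − 15 = 30, a threefold margin, and the per-category wording fails.

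**2. Eta squared against f.** f = √(η²/(1 − η²)).
- η² = 0.24 gives f = √(0.24/0.76) = 0.56.
- f = 0.40 gives η² = 0.16/1.16 = 0.138.

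The two figures stand in one sentence and describe different effects.

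**3. Reproducing 15 from f = 0.40 and r = 0.5.** One group with m repeated levels: λ = f²mN/(1 − r), df m − 1 and (m − 1)(N − 1).
- m = 3, N = 15: λ = 0.16 × 3 × 15/0.5 = 14.4, df 2 and 28, power 0.906.
- m = 3, N = 14: λ = 13.44, df 2 and 26, power 0.882.

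So 15 reproduces as a total for one group with three repeated levels. That fits neither mutually exclusive responder categories nor an on/off factor.

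**4. On versus off within one category, f = 0.40** (same formula, m = 2).
- n = 15, r = 0.5: λ = 0.16 × 2 × 15/0.5 = 9.6, df 1 and 14, power 0.82.
- n = 18, r = 0.5: power 0.892; n = 19: power 0.909. Nineteen are needed.
- n = 15, r = 0.60: λ = 4.8/0.40 = 12.0, power 0.896.
- n = 15, r = 0.62: λ = 4.8/0.38 = 12.6, power 0.910.

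Fifteen per category therefore suffices only if r is about 0.61 to 0.62 or more.

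**5. One-way comparison of three categories.** λ = f²N, df 2 and N − 3.

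| f | N | λ | Power |
|---|---|---|---|
| 0.56 (f² = 0.316) | 42 | 13.26 | 0.890 |
| 0.56 | 45 | 14.21 | 0.913 |
| 0.56 | 36 | 11.37 | 0.830 |
| 0.40 (f² = 0.16) | 45 | 7.20 | 0.635 |
| 0.40 | 84 | 13.44 | 0.907 |

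With f = 0.56 this test needs exactly 15 per category. It leaves the stated f and r unused, however, and it tests differences between categories rather than a change within subjects.

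**6. Enrolment.** For 45 completers at 20% loss: 45/0.8 = 56.25, so 57 enrolled. For 100 enrolled: 100 × 0.8 = 80 completers.

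**The case against.** The strongest defence is that 15 per category can be derived. The stated eta squared, converted correctly, gives exactly 15 per category in a one-way comparison over the three categories that section 7c names. On/off testing within a category of 15 also passes 90% once r is slightly above 0.60, which lies inside the stated range of at least 0.5. Both points stand. A reader who takes only f = 0.40 with r = 0.5 might infer that 15 can arise only as a total; the other stated inputs do not support that.

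Neither route rescues the text. Each makes 45 the bare requirement, so the allowance sentence is then false. The first also drops two stated inputs and tests something other than the stated aim. The second needs a value of r that the SAP does not fix.

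It can also be said that 45 is worded as the number to finish the protocol, hence completers. But a count of completers cannot at the same time absorb attrition and incomplete measurements, which is what the same sentence claims.

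Finally, the target is 100, well above 45. That stands, and it limits the consequence.

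**Conclusion.** The sample size justification is wrong as written. The allowance inside 45 is 0 if 15 is per category and 30 if 15 is a total, and no reading makes both sentences true. The stated eta squared and f are incompatible (0.24 against 0.138, or f of 0.56 against 0.40), and each leads to a different meaning of 15. Depending on which is used, 45 patients give a one-way comparison power of 0.913 or 0.635.

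The wording conflict follows from the text alone. The power figures rest on equal categories and, where a correlation enters, on the r shown.

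A reader might infer that the trial is too small. The documents do not support that. The extra subjects for sex and BMI are measured on the same outcome, and 100 enrolled leaves about 80 completers at 20% loss. The 84 needed for a one-way test at f = 0.40 belongs to one possible calculation that the SAP does not say it used. What is shown is an untraceable power claim, not a shortfall in the target of 100.

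**What to change.** In section 7c:

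1. Reconcile eta squared with f and state which was used.
2. State the design, the effect tested and the value of r, then recompute 15 and say whether it is per category or a total.
3. If it is per category, restate 45 (or the recomputed figure) as the completers required, with 57 enrolled at 20% loss, and delete the claim that 45 covers sex, attrition and incomplete measurements.
4. If it is a total, delete the per-category wording.
5. In either case keep the target at 100, state about 80 expected completers at 20% loss, and give the power for that number under the chosen design.

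The cost is one recalculation and a few reworded sentences. The correction of the wording itself requires no additional subjects.

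### The effect size, the 15 subjects per responder category at 90% power, and the allowance claimed within 45 subjects cannot all hold together (SAP section 7c)

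*SAP*

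**What the plan says.** The sample size is justified in one paragraph of SAP section 7c.

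- **Design:** "Using an ANOVA framework for estimating sample size for a 1x3 factorial design (Specific Aim A: complete responder, partial responder, and non-responder").
- **Target:** "we calculate the sample required to detect within-subject changes in upper airway function", illustrated by a fall in P_CRIT of about 3.5 ± 2.0 cmH2O under stimulation.
- **Effect size:** this response is put at about 24% "of the total variance", "which yields an effect size (f) of ~ 0.40".
- **Correlation:** "Our data also demonstrate within-subject correlations of at least 0.5 for repeated" P_CRIT measurements.
- **Result:** "15 subjects would be required to detect significant differences in each of 3 responder categories with an alpha of 0.05 and a power of 90" per cent.
- **Enlargement:** "To account for measurements in both sexes, subject attrition, and incomplete measurements, we propose an 'n' of 45 subjects to complete the protocol". Examining sex and BMI is then added, "which will require an additional 30-60 subjects (total n = 100) for the entire protocol".

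Two other places bear on this. The opening of section 7 makes stimulation status, on versus off, the primary independent variable. Section 4b expects about 20% of participants not to complete all visits.

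**The concern.** Three links in the paragraph fail or cannot be followed.

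1. The stated share of total variance does not convert to the stated f.
2. Complete, partial and non-responders are different people, so category is a between-subject factor. The change being sized has two within-subject levels, on and off. With the stated f and correlation, 15 subjects per category do not give 90% power for that change in a two-sided test.
3. The 45 is exactly three times 15, yet it is presented as already containing an allowance.

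At stake is whether the power claim at the 45-subject stage can be relied on, and whether that stage can absorb any loss of subjects. Total enrolment is not at stake.

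**Working it through.** **Inputs from SAP section 7c:** eta-squared 0.24; f = 0.40; correlation rho = 0.5 (stated as a minimum); alpha 0.05; power 90%; n = 15; then 45 and 100. From section 7: two stimulation levels. From section 4b: 20% non-completion.

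**Assumptions:** two-sided testing unless noted, sphericity where there are three repeated conditions, and equal categories. The plan states none of these.

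**Formulas.** N = subjects, m = repeated conditions, k = groups.
- Within-subject effect: noncentral F with lambda = f² x N x m / (1 − rho), df = m − 1 and (N − k)(m − 1).
- One-way comparison of k groups: lambda = f² x N, df = k − 1 and N − k.

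**Step 1. Routes that return 15.**

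| Route | Calculation | Power |
|---|---|---|
| 15 in total, one group, three repeated conditions, f = 0.40, rho = 0.5 | lambda = 0.16 x 15 x 3 / 0.5 = 14.4; df 2, 28 | 90.6% (88.2% at 14) |
| 15 in total, as three groups of 5, same inputs | lambda = 14.4; df 2, 24 | 90.0% |
| 15 per category, one-way ANOVA on three groups, f = 0.562 | lambda = 0.3158 x 45 = 14.2; df 2, 42 | 91.3% (89.0% at 14 per group) |
| 15 per category, one-sided paired on/off test, f = 0.40, rho = 0.5 | standardised change = √(9.6/15) = 0.80 | 90.3% (88.2% at 14) |

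So 15 can be reproduced, but by routes that conflict. The first two make it a total and need a three-level repeated factor, whereas the primary factor has two levels. The third makes it per category, but drops the correlation, replaces the printed f and compares categories instead of testing a within-subject change; with the printed f = 0.40 that comparison has 63.5% power at 45. The fourth needs a one-sided test, which the text does not state.

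**Step 2. Effect-size conversion.**
- 24% of total variance: f = √(0.24/0.76) = 0.562.
- Reverse: f = 0.40 gives 0.16/1.16 = 13.8% of total variance.
- Partial, within-subject, at rho = 0.5: 0.16/(0.16 + 0.50) = 0.242. On this reading alone, 24% and 0.40 agree.

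**Step 3. On/off change within one category (m = 2, k = 1), f = 0.40, rho = 0.5.** At n = 15, lambda = 0.16 x 15 x 2 / 0.5 = 9.6, df 1, 14.

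| n in the category | Power |
|---|---|
| 12 | 71.4% |
| 15 | 82.1% |
| 18 | 89.2% |
| 19 | 90.9% |
| 26 | 97.5% |
| 27 | 97.9% |

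**Step 4. Sensitivity at n = 15.**
- rho = 0.60: 89.6%; rho = 0.606: 90%; rho = 0.70: 96.0%
- one-sided: 90.3%
- f = 0.562, rho = 0.5: 98.1% (11 subjects suffice for 90%)

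**Step 5. The allowance.** 3 x 15 = 45, which leaves nothing over. With 20% non-completion, 15 x 0.8 = 12 per category, or 71.4% power at f = 0.40, rho = 0.5. If 15 is a total, 45 is a threefold enlargement, but the figure then does not apply in each category.

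**Step 6. Power for the whole sample (m = 2, k = 3, f = 0.40, rho = 0.5).** At 45 subjects: overall on/off 99.9%, category-by-stimulation interaction 99.8%. At 100 x 0.8 = 80 completers: both above 99.9%.

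**The case against.** The strongest reply is that 82% is one corner of the printed inputs. It needs f at 0.40, the correlation at its stated minimum, a two-sided test and a separate test in each category. Move any of these and the shortfall shrinks or disappears: 98.1% at f = 0.562, about 90% at a correlation of 0.61 or one-sided, and 85.7% with error pooled over all 45 subjects (lambda 9.6, df 1, 42). If the 3.5 ± 2.0 is read as mean and SD of the change (the text does not say so), the standardised change is 1.75 and power exceeds 99.9%. This stands: 82% must be quoted with its conditions and is not the single corrected value.

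A reader might also infer that the authors took a three-condition total and wrongly assigned it to each category, or that 15 can arise only in that way. The document does not support either. The one-way and one-sided routes also give 15 per category, and the text does not say which calculation was run.

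What the reply does not remove is the inconsistency. Rescuing 90% through f = 0.562 rejects the printed f; the one-sided route adds a condition the text does not give; a higher correlation is not stated. No choice makes 24% of total variance equal f = 0.40, or finds an allowance in 3 x 15 = 45.

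**Conclusion.** The point holds as an inconsistency within one paragraph. The conversion from 24% of total variance to f = 0.40 is wrong unless the 24% is partial eta-squared at a correlation of 0.5. If f = 0.40 and rho = 0.5 are kept with a two-sided test, 15 per category gives about 82% for the on/off change, not 90%, and 19 are needed. If f is corrected to 0.562 instead, 15 gives about 98%. Separately, either 45 contains no allowance or 15 does not belong to each category; this needs no power assumption.

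A reader might conclude that the study is underpowered. The figures do not support that. At f = 0.40, rho = 0.5 and equal categories, overall on/off power is 99.9% at 45, and on/off power within a category is 97–98% with 26–27 subjects, which is what about 80 completers of 100 would provide. The defect lies in the stated basis for the 45-subject stage. It should be fixed, and fixing it is cheap.

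**What to change.** Rewrite the sample-size paragraph of SAP section 7c:

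1. Label the 24% as partial, within-subject eta-squared, or correct f to 0.56.
2. Name the test and its sidedness, and say whether 15 is a total or a number per category.
3. Recompute with stimulation (on/off) within subject and responder category between subjects. Add the category-by-stimulation interaction if differences between categories are the target.
4. If 15 is per category, stop describing 45 as including attrition. If it is a total, remove the attribution to each category.
5. Restate power at 45 and at about 80 completers of 100, giving the assumed f, correlation and category split.

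The cost is one paragraph, with no added enrolment. The downside is a less favourable stated per-category power at 45 (about 82%) if f = 0.40, a correlation of 0.5 and a two-sided test are kept.
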